- MRI-PDFF percent change and change from Baseline at Week 26. This secondary efficacy endpoint will be compared between treatment groups using a one-sided Wilcoxon rank-sum test. An analysis of covariance (ANCOVA) model will also be used with percent change and change from baseline as the dependent variable; treatment group, T2DM status (yes, no), region (North America, not North America), and amount of fibrosis (F2, F3) as factors; and Baseline as a covariate. Least-squares (LS) means and their differences will be estimated from the ANCOVA model and their corresponding 95% CI will be derived. Inferential statistics will be presented for both the ANCOVA model and the Wilcoxon test. For the continuous secondary endpoints with sufficient postbaseline frequency of measurements, a mixed model repeated measure (MMRM) model will also be employed.
- MRI-PDFF percent change and change from Baseline at Week 52. This secondary endpoint will be analyzed similarly to MRI-PDFF percent change and change from Baseline at Week 26, as described above.
- Proportion of subjects with NASH resolution at 52 weeks. Treatment groups will be compared based on this secondary efficacy endpoint using an analysis similar to the primary efficacy endpoint.
- Change from Baseline in ALT, AST, and GGT at Weeks 26 and 52 and at each study visit. This secondary endpoint will be analyzed similarly to MRI-PDFF percent change and change from Baseline at Week 26, as described above.
- Change from Baseline in LDL-C and other lipid levels at Weeks 26 and 52 and at each study visit. This secondary endpoint will be analyzed similarly to MRI-PDFF percent change and change from Baseline at Week 26, as described above.
- Change from Baseline in collagen/fibrous area and fibrosis score, assessed by digital pathology, at Week 52. This secondary endpoint will be analyzed similarly to MRI-PDFF percent change and change from Baseline at Week 26, as described above.
- Changes from Baseline in metabolic parameters, including fasting insulin, fasting glucose, HOMA-IR, adipo-IR, and HbA1c levels at Weeks 26 and 52 and at each study visit. This secondary endpoint will be analyzed similarly to MRI-PDFF percent change and change from Baseline at Week 26, as described above.

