4.2. Randomization and Blinding

This will be a double-blind, randomized study. Subjects will be centrally assigned to randomized study treatment using an Interactive Web-based Response System (IWRS).

Approximately 162 unique subjects with liver fibrosis stage F2-F3 will be enrolled and randomized (2:1 ratio) to receive TVB-2640 50 mg or placebo (approximately 108 for TVB-2640 50 mg and approximately 54 subjects for placebo) PO QD for 52 weeks. Dynamic allocation is used for the randomization, stratified by T2DM status (Yes, No), region (North America, not North America), and amount of fibrosis (F2 or F3).

All subjects, Investigators, the Sponsor, and the clinical research organization (CRO) will be blinded to the treatment assignment of each individual subject. Members of the IDMC and the IDMC's independent statistician will be unblinded to treatment assignment as needed. In addition, specific vendors whose role in study conduct requires them to be unblinded (e.g., personnel operationally associated with the IWRS) may also be unblinded.

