9. EFFICACY

9.1. Primary Efficacy Endpoint Analyses

9.1.1. Principal Analysis of the Primary Efficacy Endpoints

The principal efficacy analyses will be conducted on the ITT population. Additional sensitivity and supplementary analyses will be performed for the primary efficacy endpoints, as described in the next section.

The treatment groups will be compared based on the primary efficacy endpoints using one-sided Cochran-Mantel-Haenszel (CMH) tests stratified by the randomization stratifications T2DM status at baseline (yes or no) and amount of fibrosis at baseline (F2 or F3).

Mathematically, the null and alternative hypotheses for the primary efficacy endpoints are stated as:

$$H_0: p_T \leq p_p$$

$$H_a: p_T > p_p$$

Where, p_T is the proportion of responders in the TVB-2640 50-mg treatment group and p_p is the proportion of responders in the placebo treatment group. The higher responder proportion is a better outcome.

A Clopper-Pearson 90% and 95% CI will be derived for each treatment group, and the stratified CMH odds ratio (with its 90% and 95% CI, using the control group as a reference group) will be produced to assess the treatment effect magnitude. The difference in treatment groups response rates will be provided and also be characterized by the 90% and 95% CIs using Miettinen and Nurminen (1985).

Subgroup analyses of the primary efficacy endpoints will be performed to assess whether the treatment effect is concordant among subgroups. The planned subgroup analyses are described in Section 7.2. Analyses will be performed if there is an adequate number of subjects in each subgroup.

A subject who discontinues treatment prior to Week 42, does not provide a histological assessment on or after Week 42, or who otherwise has missing data will be considered a non-responder.

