9.1.2. Sensitivity Analyses of the Primary Efficacy Endpoints

Evaluation of the robustness of the principal analysis of the primary efficacy endpoints will be carried out using the following (4) four approaches:

- A logistic regression with response as a dependent variable; treatment group, randomization stratification factors (T2DM status at baseline [yes or no] and amount of fibrosis at baseline [F2 or F3]) as independent factors; and age as a baseline covariate.
- The analysis of the primary efficacy endpoints will be repeated for the modified Intention-to-Treat (mITT) population to ascertain any changes in the conclusion of the principal analysis findings.
- A repeat of the primary efficacy analysis principal analysis (CMH test) for the following three ITT subsets:
 - ITT Subjects who achieve at least 50% of total cumulative study drug dose (i.e., at least **9100 mg** 52-week total dose (based on a total of 50 mg.kg x 52 weeks x 7 days = 18200 mg x weeks x days).
 - ITT Subjects who achieve at least 70% of total cumulative study drug dose (i.e., at least **12740 mg** 52-week total dose (based on a total of 50 mg x 52 weeks x 7 days = 18200 mg x weeks x days).
 - ITT Subjects who achieve at least 80% of total cumulative study drug dose (i.e., at least **14560 mg** 52-week total dose (based on a total of 50 mg.kg x 52 weeks x 7 days = 18200 mg x weeks x days).
- To assess the impact of missing data in the primary endpoint analyses, multiple imputation procedure will be carried out using MAR assumption with Fully Conditional Specification method for binary endpoint in SAS PROC MI. 100 imputations will be performed. The CMH test statistic from each imputed dataset will be based on Wilson-Hilferty transformation (Wilson & Hilferty, 1931) and will be combined using PROC MIANALYZE. Combined CMH test statistic and p-value will be computed. The method described in Ratitch, Lipkovich, and O'Kelly (2013) will be used to combine the results.

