9.2. Secondary Efficacy Endpoints and Analyses

Secondary efficacy analyses for the other histological responder endpoints will be analyzed in the ITT and mITT populations using the methods described for the primary efficacy endpoint.

Secondary efficacy analyses of endpoints expressed as percent change or change from Baseline only at Week 26 or only at Week 52 will be analyzed in the ITT analysis set using an analysis of covariance (ANCOVA) model with fixed effects for T2DM status at baseline (Yes, No) and treatment group, and a covariate term for baseline analysis value of response. Least squares (LS) means for the percent change from Baseline by treatment and the associated standard errors, the

LS means for the difference between treatment groups, and the associated two-sided 95% CIs and two-sided p-values, based on t-tests, will be derived from the ANCOVA model.

For secondary endpoints assessed at multiple visits, a linear mixed-effects model for repeated measures (MMRM) may be used. The model will include T2DM status at baseline (Yes, No), treatment group, visit, and treatment-by-visit interaction as the fixed effects, and baseline value as a covariate, and the model will use an unstructured variance-covariance matrix. The point estimates for the least-squares mean of the difference treatment groups at each visit and the corresponding 95% confidence interval and two-sided p-value will be summarized. If convergence problems arise when fitting the model, a spatial power covariance structure will be used as a first step. If the model still has convergence issues, compound symmetry covariance structure will be employed. The Kenward-Roger correction for the denominator degrees of freedom will be applied.

ALT, AST, ALP, and GGT will also be summarized in shift tables of baseline to each visit based on range categories of low (below lower limit of normal [LLN], normal, and high [above upper limit of normal [ULN]]).

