The continuous digital pathology variables (qFibrosis, qSteatosis, and Steatosis corrected qFibrosis) will be summarized descriptively with change from baseline being analyzed using MMRM methods. Digital pathology stage/grade variables (qFibrosis – stage, qSteatosis – grade, and Steatosis corrected qFibrosis – stage) will be summarized descriptively with change from baseline being analyzed using ANCOVA methods. The ANCOVA models will include fixed effects for treatment group, T2DM status at baseline (Yes, No), and amount of fibrosis at baseline (F2 or F3), and baseline value as a covariate. Shifts in stage from baseline to each visit will also be presented. The shifts will include decrease in stage, no change in stage, and increase in stage. The shifts will be compared between treatment groups using a CMH-row mean scores test.

Graphical display for selected secondary endpoints will be provided.

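### SAP 9.2 drops fibrosis stage (F2/F3), a randomisation factor, from the general ANCOVA and the MMRM for continuous secondary endpoints, and Section 11 does not disclose it

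*SAP*

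**What the plan says.** SAP 4.2 describes dynamic allocation "stratified by T2DM status (Yes, No), region (North America, not North America), and amount of fibrosis (F2 or F3"). Protocol 13.2.2 sets out the ANCOVA for MRI-PDFF change with "treatment group, T2DM status (yes, no), region (North America, not North America), and amount of fibrosis (F2, F3) as factors" and the baseline value as covariate; the synopsis gives the same terms. Protocol 13.2.2 then applies that analysis to the liver enzymes, lipids, digital pathology, metabolic markers, NASH biomarkers, FibroScan/CAP, PRO-C3 and ELF. It also foresees an MMRM where there are enough visits, but lists no terms for it.

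SAP 9.2 has two general models for continuous secondary endpoints:

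- For endpoints analysed at a single visit, an ANCOVA: "model with fixed effects for T2DM status at baseline (Yes, No) and treatment group, and a covariate term for baseline analysis value of response".
- For endpoints with several visits, an MMRM that may be used: "The model will include T2DM status at baseline (Yes, No), treatment group, visit, and treatment-by-visit interaction as the fixed effects", plus the baseline value as covariate.

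Fibrosis stage is in neither. Elsewhere the SAP keeps it:

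- Primary CMH test (9.1.1): "stratified by the randomization stratifications T2DM status at baseline (yes or no) and amount of fibrosis at baseline (F2 or F3").
- Logistic sensitivity model (9.1.2): "randomization stratification factors (T2DM status at baseline [yes or no] and amount of fibrosis at baseline [F2 or F3]) as independent factors".
- ANCOVA for digital-pathology stages and grades (later in 9.2): "fixed effects for treatment group, T2DM status at baseline (Yes, No), and amount of fibrosis at baseline (F2 or F3").

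SAP Section 11 names region as a term removed from every analysis. It does not mention fibrosis stage.

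**The concern.** When allocation is balanced on a factor and the analysis leaves that factor out, a linear model's standard error still carries the variance the factor explains, although the design has already removed that variance from the treatment comparison. If the factor is prognostic beyond the terms in the model, the standard error is too large, the test falls below its nominal level and power is lost. If it is not prognostic, nothing is lost.

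There is also a question of record. The protocol and the SAP give different ANCOVA models for the same endpoints, and the section that exists to list such changes lists one removed term but not the other. With no reason given, and with fibrosis stage kept in the SAP's other models, this reads as an oversight rather than a decision.

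SAP 9.2 is also uneven within itself. The staged qFibrosis result is adjusted for F2/F3, but for the continuous version, "The continuous digital pathology variables (qFibrosis, qSteatosis, and Steatosis corrected qFibrosis) will be summarized descriptively with change from baseline being analyzed using MMRM methods", and the only MMRM terms given omit it.

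**Working it through.** **1. Model terms side by side**

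| Analysis | T2DM | Fibrosis stage | Region |
|---|---|---|---|
| Allocation (SAP 4.2) | yes | yes | yes |
| Protocol ANCOVA (13.2.2) | yes | yes | yes |
| Protocol MMRM (13.2.2) | terms not listed | terms not listed | terms not listed |
| SAP primary CMH (9.1.1) | yes | yes | removed, disclosed |
| SAP logistic model (9.1.2) | yes | yes | removed, disclosed |
| SAP digital-pathology stage/grade ANCOVA (9.2) | yes | yes | removed, disclosed |
| SAP general ANCOVA (9.2) | yes | **no, not disclosed** | removed, disclosed |
| SAP MMRM (9.2) | yes | **no** | removed, disclosed |

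For the ANCOVA this departs from a model written in the protocol. For the MMRM there is no protocol model to depart from; the point is that an allocation factor is missing. Endpoints that the protocol would analyse with the F2/F3-adjusted ANCOVA, and that the SAP moves to the MMRM, lose the term on the way.

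**2. The planned sample size, for context**

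Inputs (SAP 4.3): 40% vs 20%, one-sided 0.05, power 80%, 2:1, dropout 18.5%. With the unpooled normal approximation:

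- Placebo n = (1.645 + 0.842)² × (0.20×0.80 + 0.40×0.60/2) / 0.20² = 6.18 × 0.28 / 0.04 = 43.3, rounded up to 44.
- Total = 3 × 44 = 132, and 132 / 0.815 = 161.96, rounded up to 162.

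The stated N is reproduced. It rests on the binary primary endpoint, whose CMH test keeps fibrosis stage, so it does not change. The 132 completers are used below.

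**3. Effect of the omission in a linear model**

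Let R² be the share of residual variance, after T2DM and the baseline value, that F2/F3 explains. The documents give no value, so 0, 1, 5 and 10% are assumed.

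- Standard-error factor f = 1/√(1 − R²)
- True two-sided level = 2 × [1 − Φ(1.960 f)]
- Two-sided power, from 80% = Φ(1.960 + 0.842 − 1.960 f)
- One-sided 5% power, from 80% = Φ(1.645 + 0.842 − 1.645 f)

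| R² | SE increase | True level (nominal 5%) | Power, two-sided | Power, one-sided |
|---|---|---|---|---|
| 0% | 0% | 5.0% | 80.0% | 80.0% |
| 1% | 0.5% | 4.9% | 79.7% | 79.8% |
| 5% | 2.6% | 4.4% | 78.5% | 78.8% |
| 10% | 5.4% | 3.9% | 76.9% | 77.4% |

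**4. Simulation check**

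Twenty thousand runs per R²; N=162; 2:1 minimisation on three factors (assumed prevalences 60, 30 and 50%); 18.5% random dropout; ANCOVA at one time point; two-sided 5%.

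| R² | SE ratio, without/with F2/F3 | Level without | Level with | Power without | Power with |
|---|---|---|---|---|---|
| 0% | 0.999 | 5.1% | 5.2% | 80.7% | 80.5% |
| 1% | 1.004 | 5.0% | 5.1% | 80.1% | 80.2% |
| 5% | 1.025 | 4.4% | 4.8% | 78.4% | 79.9% |
| 10% | 1.054 | 4.2% | 5.0% | 77.4% | 80.4% |

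A separate simulation with 132 evaluable subjects and an assumed standardised effect of 0.5 agrees. Power without vs with the term was 74.8 vs 76.4% at R² = 5% and 73.3 vs 76.7% at 10%; the level was 4.6 vs 5.1% and 4.1 vs 5.1%.

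**5. Cost of including the term if it is worthless**

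With 132 completers the residual degrees of freedom fall from 128 to 127, and power by the noncentral t falls from 80.00% to 79.995%. With an assumed 80 subjects for MRI-PDFF (76 to 75 df) it falls to 79.99%.

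**The case against.** The strongest reply is that the finding reaches too far. SAP 9.2 restricts its ANCOVA to endpoints analysed at one visit. In the SAP 7.4 table that means MRI-PDFF change at Weeks 26 and 52, because digital pathology has its own rules. Everything else goes to an MMRM, for which the protocol wrote no terms, so no written MMRM specification was changed. The distinction is right and is kept here. It does not confine the point to MRI-PDFF, because protocol 13.2.2 assigns the F2/F3-adjusted ANCOVA to the multi-visit endpoints as well, and the SAP's replacement model does not carry the term.

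SAP 7.1 says that only selected models use the strata. That shows not every model was meant to include them, but it neither discloses nor explains removing a term the protocol specified. Section 11 leaves additional changes to the CSR; that most naturally covers later changes, not one already written into the SAP.

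SAP 7.2 makes fibrosis stage a subgroup factor for the liver enzymes. This does not by itself require adjustment in the overall model, and nothing here rests on it.

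The objection on size largely stands. At R² of 0 to 1% the simulated differences are Monte Carlo noise, a loss of about 3 points needs an assumed 10%, and the calculations are for a single-visit linear model. No MMRM was simulated. MRI-PDFF numbers will also be below 132, since some sites do not perform the scan and it is optional in cases of hardship.

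**Conclusion.** The concern holds, as a minor one. Fibrosis stage is an allocation factor, is in the protocol's ANCOVA, is missing from both general models in SAP 9.2, and is not among the changes in Section 11. Under the assumed range of 0 to 10% of residual variance, omission costs between nothing and about 3 points of power on the affected secondary endpoints. The error is conservative: the true two-sided level lies between 5.0 and 3.9%, so no false-positive risk is added. The primary analysis and the sample size are unaffected. The discrepancy between the two documents, and its absence from Section 11, remain whatever the prognostic value of fibrosis stage turns out to be.

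**What to change.** In SAP 9.2, add baseline fibrosis stage (F2/F3) as a fixed effect to the general ANCOVA and to the MMRM. This brings both into line with the digital-pathology stage/grade ANCOVA in the same section and restores the protocol's fibrosis term for the ANCOVA. If the sponsor prefers to leave it out, Section 11 should list the omission and give the reason.

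As an editorial correction, SAP 7.1 announces three randomisation factors but names two; region should be added. The CMH stratification and the logistic model can stay as they are, since the removal of region is disclosed.

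The cost is a few words in the SAP and one model term already recorded at randomisation. It needs no new data and no change in sample size. It should be settled before unblinding, the point by which SAP Section 2 requires the final version.

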7. GENERAL DATA HANDLING CONSIDERATIONS

All analyses will be conducted using SAS software Version 9.4 or higher.

All data in the database will be presented in by-subject data listings. Unless otherwise stated, all listings will be sorted by treatment group, center ID, subject number, and assessment date and time, if available.

Unless stated otherwise, continuous data will be summarized by treatment group using descriptive statistics including number of subjects (n), mean, median, standard deviation (SD), first quartile (Q1), third quartile (Q3), minimum (min) value, maximum (max) value.

Unless stated otherwise, categorical data will be summarized by treatment group using counts and percentage based on the number of non-missing values. For selected summaries, the number of missing values will be presented as a separate category with no percentage, if one or more subjects have missing data. Counts of zero will be presented without percentages.

Descriptive statistics will be presented with the following numerical precision:

- Minimum and Maximum: same as the raw data collected
- Mean, Median, Q1, and Q3: one additional decimal place to that reported for Minimum and Maximum
- SD: two additional decimal places than the Minimum and Maximum
- Percentages: reported to one decimal place if percent is <100. If the value is 100, no decimal place will be reported.

Unless otherwise noted, statistical inference will be based on two-sided testing with a 5% significance level. Confidence intervals will be at the 90% and 95% levels.

P-values will be reported to four decimal places. If the value is below 0.0001 it will be noted as < 0.0001; if the value above 0.9999 it will be noted as > 0.9999.

All data up to the time of study completion/withdrawal from the study will be included in the analysis, regardless of duration of treatment.

Numbering for data displays will be based on [International Council for Harmonization \(ICH\) E3](#) whenever possible.

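### SAP 9.2's MMRM fallback structures assume equal residual variance at every visit; if variance rises over time, the Week 52 test of multi-visit secondary endpoints is anti-conservative

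*SAP*

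**What the plan says.** SAP 9.2 states that for secondary endpoints assessed at multiple visits "a linear mixed-effects model for repeated measures (MMRM) may be used". The model has T2DM status, "treatment group, visit, and treatment-by-visit interaction as the fixed effects, and baseline value as a covariate", and at the outset "the model will use an unstructured variance-covariance matrix". At each visit the treatment difference is reported and the "corresponding 95% confidence interval and two-sided p-value will be summarized".

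Two sentences cover non-convergence: "If convergence problems arise when fitting the model, a spatial power covariance structure will be used as a first step", then "If the model still has convergence issues, compound symmetry covariance structure will be employed". The paragraph ends: "The Kenward-Roger correction for the denominator degrees of freedom will be applied". It names no heterogeneous-variance version of either structure and no empirical (sandwich) standard error.

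The default level in SAP 7 is that "statistical inference will be based on two-sided testing with a 5% significance level". SAP 7.4 assigns one-sided tests to some continuous endpoints, for example FibroScan and CAP.

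**The concern.** With six post-baseline visits, an unstructured matrix has 6 × 7 / 2 = 21 parameters. Spatial power and compound symmetry have two each: one variance and one correlation parameter. The rule therefore gives up every visit-specific variance in one step, with nothing in between.

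Rising variance is plausible here. The outcome is change from baseline with baseline as a covariate. If the raw variance is stable, residual variance at visit t is proportional to 1 − r(t)², where r(t) is the correlation with baseline. If r(t) weakens between Week 4 and Week 52, residual variance grows. A pooled variance is then too small at Week 52 and too large at Week 4. Kenward-Roger adjusts degrees of freedom and small-sample bias within the chosen structure; it does not repair the structure.

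At stake are the Week 52 p-values and 95% intervals for liver enzymes, lipids, metabolic markers, PRO-C3 and similar endpoints. SAP 9.2 gives ANCOVA to endpoints expressed at a single time point, so for multi-visit endpoints the MMRM is the only inferential model it names.

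**Working it through.** **The plan's own figures.** The documents give no error rate for this step and no SD or correlation for any continuous endpoint. The one design figure, N = 162, reproduces: (1.645 + 0.842)² × (0.4×0.6/2 + 0.2×0.8) / 0.2² = 43.3, so 44 placebo + 88 active = 132, and 132 / (1 − 0.185) = 162. It enters below only as the trial size.

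**Inputs from the documents.** 108 and 54 subjects and 18.5% dropout (SAP 4.3); visits at Weeks 4, 8, 13, 26, 39, 52 (SAP 4.1); the model terms of SAP 9.2. **Assumed:** the pattern of SDs or correlations over visits.

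**Closed form.** Let k = true residual SD at a visit / SD pooled over visits. A nominal 5% two-sided test with the pooled SD rejects at 2 × (1 − Φ(1.96/k)).

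- k = 1.00: 5.0%
- k = 1.12: 1.96/1.12 = 1.75, giving 8.0% (95% interval covers about 92%)
- k = 1.33: 1.96/1.33 = 1.474, giving 14.1% (covers about 86%)

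**What correlations produce such a k.** Take variance 1 − r(t)² with r linear in time. For r from 0.80 to 0.65 the six variances are 0.360, 0.380, 0.404, 0.465, 0.523 and 0.578, with mean 0.452. So k at Week 52 is √(0.578/0.452) = 1.13.

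| r, Week 4 to Week 52 | k, Week 52 | Week 4 | Week 26 | Week 52 | Mean of six visits |
|---|---|---|---|---|---|
| 0.80 to 0.65 | 1.13 | 2.8% | 5.4% | 8.3% | 5.1% |
| 0.85 to 0.50 | 1.24 | 1.0% | 6.0% | 11.5% | 5.3% |
| 0.90 to 0.40 | 1.32 | 0.2% | 6.6% | 13.7% | 5.7% |
| 0.70 to 0.65 | 1.04 | 4.4% | 5.1% | 5.9% | 5.0% |
| flat | 1.00 | 5.0% | 5.0% | 5.0% | 5.0% |

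If r falls in equal steps per visit instead, the first three Week 52 rates are 7.7%, 9.9% and 11.3%.

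**Simulation of the SAP model.** REML fits with model-based errors, no treatment effect, 3,004 trials per setting. SD is linear in time, and the true correlation is either exchangeable (0.5) or decaying (0.6 per 13 weeks). A t reference with 158 df stands in for Kenward-Roger. Monte Carlo error is about 0.4 to 0.7 points. Ranges are over the two true correlations; the Week 4 column also spans both fallbacks.

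| SD Week 52 / Week 4 | k, Week 52 | Week 52, spatial power | Week 52, compound symmetry | Week 4 |
|---|---|---|---|---|
| 0.7 | 0.79 | 1.0–1.5% | 1.3–1.7% | 7.1–7.8% |
| 1.0 | 1.00 | 4.6–4.7% | 5.3–5.4% | 3.9–5.6% |
| 1.25 | 1.13 | 7.8% | 8.5–9.5% | 3.0–3.4% |
| 1.5 | 1.23 | 9.7–10.2% | 11.6–11.9% | 1.7–2.2% |
| 2.0 | 1.38 | 12.6–15.0% | 15.9–17.5% | 0.3–0.5% |

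With only two visits (Weeks 26 and 52), SD ratios of 1.0, 1.25 and 1.5 give 5.4%, 8.3% and 10.1% at Week 52 under either structure. One-sided 5% tests inflate less: 8.0–8.7% (spatial power) and 9.1–10.0% (compound symmetry) at six visits and ratio 1.5.

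**Remedies, at Week 52.**

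- Heterogeneous compound symmetry: 5.0% at ratio 1.5; 5.7% or 3.0% at ratio 2.0 (exchangeable or decaying truth).
- Heterogeneous spatial power: 5.8%; 7.2% or 3.7%. Both heterogeneous checks used 764 to 995 trials, Monte Carlo error 0.6 to 0.9 points.
- Sandwich errors on the homogeneous fallbacks: 4.5% to 6.0% across runs at 108/54. In a rough run with compound symmetry and r from 0.85 to 0.50, the rate was 7.7% at 24/12.
- A Week 52-only ANCOVA: 4.0% to 5.8% in the settings above.

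Heterogeneous Toeplitz was not simulated.

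**The case against.** The strongest objection is that the rule may never matter. The MMRM is optional and the fallback needs a failed unstructured fit. With about 162 subjects and at most 21 covariance parameters, failure is not shown to be likely; FibroScan, CAP and ELF have two post-baseline time points and need only three. The endpoints are secondary, and SAP 7.3 provides no multiplicity control for them, so no formal decision rests on their p-values. Protocol 13.2.2 also plans Wilcoxon and ANCOVA for the continuous secondary endpoints, with MMRM as an addition. All of this stands and keeps the point small. The backstop is uncertain, though: SAP 9.2 does not repeat those analyses for multi-visit endpoints, and SAP 11 does not list their removal.

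A reader might infer that the fallback by itself makes the Week 52 test reject at 8% to 14%. The documents do not support that: the rate depends on an SD pattern they do not give, and equal or falling variances give about 5% or less. A reader might also infer that false positive biomarker findings roughly double overall. That holds at most for Week 52. Early visits become conservative, Week 26 stays near nominal, and the mean over six visits is 5.1% to 5.7% in the three steeper correlation patterns. Nor do the documents show that skewed biomarkers or the SAP 7.2 subgroups would trigger the fallback; subgroup sizes are unknown.

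**Conclusion.** The point holds conditionally, as a cheap improvement. Both fallbacks impose equal residual variance over visits, and nothing in SAP 9.2 protects against that being wrong. Under the assumption that the Week 52 SD is 1.12 to 1.33 times the pooled SD, the two-sided Week 52 test runs at about 8% to 14%, and steeper growth takes it higher. The figures also assume normal errors, dropout unrelated to outcome, the same SDs in both arms, and a t approximation to Kenward-Roger. The scope is continuous secondary endpoints with several visits; the co-primary results are untouched.

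**What to change.** In SAP 9.2, before unblinding, place heterogeneous-variance structures ahead of any homogeneous one: for example heterogeneous Toeplitz (6 + 5 = 11 parameters at six visits), then heterogeneous compound symmetry (6 + 1 = 7), both with Kenward-Roger. If spatial power or compound symmetry is still needed as a last resort, take standard errors from the empirical (sandwich) estimator, with a small-sample correction in small subgroups.

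The cost is one SAP sentence and one program option. The downsides are somewhat wider Week 52 intervals if variance does rise, possible non-convergence of the richer structures, loss of Kenward-Roger where the sandwich is used, and slight residual inflation of the sandwich in small subgroups.
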